### **3.7 Methods: Data collection, management and analysis**

#### **3.7.1 Data Collection**

For all visits each patient will fill out a questionnaire (See Appendices for full surveys) using RedCap. If a patient is unable to enter the data using email directly, one of our research assistants will enter the data into the RedCap system via telephone interview. For the follow up survey if there is no response, we will attempt to contact the patient by phone three times. In regard to those patients seen in follow up in the clinic, we will ensure that they finish their follow up questionnaires after being seen by a healthcare professional to avoid unblinding. Patients' receiving the standard of care will be asked the same questions at week 0 and 12 with the same surveys as the education intervention arm of the study. A secure password protected master linking log will be able to house the patient name with study identification number.

#### **3.7.2 REDCap Security Summary**

The Applied Health Research Centre (AHRC), an academic research organization based at St Michael's Hospital, will use software called REDCap (<http://project-redcap.org/>) to create the web-based electronic CRF (eCRF). All study data will be securely stored on local servers at St Michaels Hospital throughout the duration of the study and for up to 10 years after the study is complete. All study subjects will be identified in the database by a unique study ID number. Linkages between the patient name/contact information and the study ID will be retained at the local site and not shared with the study DCC or outside the institution. At the end of the study (after all analyses are complete) the DCC will transfer all study datasets over to the study PI . Data will only be accessible by authorized study site personnel and authorized central DCC personnel. Authorized personnel receive a username and password which is unique, and database access is controlled by the DCC in collaboration with the Principal Investigator.

##### **3.7.2.1 Physical Access and Security**

The REDCap application is hosted locally in St. Michael's Hospitals secure data centers and has dedicated IT, database, application, and build support personnel. The SMH data centre infrastructure has several features in place to enhance the security of data, prevent data loss and mitigate downtime. These include:

- Duplicate Internet Service Providers (ISPs)

- Infrastructure distributed between two data centres
- Virtualization for added redundancy
- Data centres are accessible by designated IT staff only
- Access is logged through RFID card access and through a physical sign in page
- Redundant UPS' for backup power
- Redundant cooling systems
- Inert gas-based fire suppression system

Data will be stored on the local Storage Area Network (SAN) and will be backed up regularly and stored off-site. The data centre is designed such that there are daily backups made of all critical data. In addition, the backups are stored both locally, as well as at a remote off-site location, in the case of catastrophic failure at one location. With limited access privileges, 24 hour security, and around-the-clock monitoring, the data centre is highly secure.

### ***3.7.2.2 Logical Access and Security***

REDCap servers are accessible by designated IT staff only for administration and maintenance purposes. The REDCap application is accessible by registered (through AHRC) users only, who are restricted to accessing the projects that they are assigned to. REDCap uses standard authentication mechanisms to ensure only registered users can access the system, ensures only explicitly specified users can access any particular project and data, and furthermore, provides customizable user access for each project with controls that can be used to restrict users to write or read-only privileges on a form-by-form basis. Transmitted data is secured through the use of TLS certificates that encrypt all data sent to and from the server.

### ***3.7.3 Primary Outcomes.***

Data will be collected using the Rivermead Post Concussion Symptoms Questionnaire (RPQ): The symptoms listed on the RPQ are those most commonly reported in the published literature as post concussion syndrome (PCS). The RPCSQ is a 16-question instrument that examines post-concussion symptoms rated by the patient according to the increase in their frequency compared with premorbid levels. The total score is calculated based on 2 domains (cognitive and emotional-somatic) and ranges from 0 to 72. The RPQ has been shown to measure severity of postconcussion symptoms reliably with good test-retest and inter-rater reliability for individual symptom scores. Based on previous studies, splitting the RPQ into two subscale scores: RPQ-3 uses the sum of scores from three items

(headaches, dizziness and nausea) and RPQ-13 uses the sum of scores of the other 13 items. Higher scores especially for the RPQ-13 subscale are associated with greater impact on lifestyle. For our study significance will be observed if patients reported symptoms decreased by 3 on the RPQ-3 and 10 on the RPQ-13.

We will be comparing headache symptom reporting between the two groups assigning significance if patients in the education arm have a decrease in symptom reporting on the RPQ-3 by 3 and 10 on the RPQ-13.

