## 1 Table of Contents

1	Table of Contents	2
2	Administrative Information	4
3	Introduction	6
3.1	Background	6
3.2	Aim of the Study	8
3.3	Study Hypothesis and Objectives	8
3.3.1	Hypothesis	8
3.3.2	Primary Objective	8
3.3.3	Secondary Objectives	8
3.4	Trial Design	9
3.4.1	Post Traumatic Headache Education Study Flow Diagram	9
3.5	Methods: Participants, Measures and Outcomes	10
3.5.1	Eligibility Criteria	10
3.5.2	Interventions	10
3.5.3	Outcomes	13
3.5.4	Primary Outcome Measures	13
3.5.5	Secondary Outcome Measures	13
3.5.6	Sample Size	14
3.5.7	Recruitment	14
3.6	Methods: Assignment of Intervention	14
3.6.1	Allocation	14
3.6.2	Blinding	14
3.7	Methods: Data collection, management and analysis	15
3.7.1	Data Collection	15
3.7.2	Primary Outcomes.	16
3.7.3	Secondary Outcomes	17
3.7.4	Retention	18
3.7.5	Data Management	18
3.7.6	Statistics	18
3.8	Ethics and dissemination	18
3.8.1	Ethics	18
3.8.2	Study participants' identification	19
3.9	Appendices	19
3.10	References	19

Lists of abbreviations and terminology

mTBI: Mild Traumatic Brain Injury  
PTH: Post Traumatic Headache  
RPQ: Rivermead post-concussion questionnaire  
PART-O: Participation Assessment with Recombined Tools-Objective  
QOLIBRI: Quality of Life after Brain Injury  
REDCap: Research Electronic Data Capture

Protocol Summary:

*Full Title:* Can targeted education impact the current standard of care in patients with mild traumatic brain injury?

*Sample Size:* Approximately 70 patients

*Study Population:* Patients seen at the St. Michael's Head Injury Clinic

*Study Design:* Randomized-Control Study

*Study Duration:* January 2018- December 2019

*Study Agent/ Intervention/ Procedure:* Educational

*Primary Objective:* Are we able to see a decrease in patients reported symptoms by 3 on the Rivermead post concussion questionnaire or RPQ-3 and 10 on the RPQ-13 in those that receive targeted headache education in comparison to those who do not?

*Secondary Objectives:* When and what type of health care services do participants in this study access, how frequently and is there a difference and between the two groups.

Does education through reinforcement of appropriate lifestyle and treatment strategies translate to similar pre-injury scores on the PART-O tool at the 12-week time point.

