By the end of the study, the educational intervention group will be more satisfied in various aspects of their life as measured by the QOLIBRI compared to their week 0 scores.

*Endpoints of the study:* Significance will be observed if patients reported symptoms decrease by 3 points on the RPQ-3 and 10 on the RPQ-13.

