#### **3.3.2 Primary Objective**

Are we able to see a decrease patient reported symptoms by 3 on the Rivermead post-concussion questionnaire or RPQ-3 and 10 on the RPQ-13 in those that receive targeted headache education in comparison to those who do not?

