### **3.5.3 Outcomes**

#### **3.5.4 Primary Outcome Measures**

Targeted education provided to patients suffering from post-traumatic headache will be assessed using the RPQ. The RPCSQ is a 16-question instrument that examines post-concussion symptoms rated by the patient according to the increase in their frequency compared with premorbid levels. The total score is calculated based on 2 domains (cognitive and emotional-somatic) and ranges from 0 to 72. The RPQ has been shown to measure severity of postconcussion symptoms reliably with good test-retest and inter-rater reliability for individual symptom scores. Based on previous studies, splitting the RPQ into two subscale scores: RPQ-3 uses the sum of scores from three items (headaches, dizziness and nausea) and RPQ-13 uses the sum of scores of the other 13 items. Higher scores especially for the RPQ-13 subscale are associated with greater impact on lifestyle. For our study significance will be observed if patients reported symptoms decreased by 3 on the RPQ-3 and 10 on the RPQ-13.

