#### **3.7.7 Statistics**

The IBM SPSS statistical software will be used for the data analysis. Data will be entered on demographic factors (sex, age, ethnicity, years of education), frequency and type of health care accessed will be analyzed as well. Scores on the Rivermead, PART-O and QUOLIBRI will be analyzed and comparisons will be made between the educational arm and the current standard of care group. We will be using univariate Chi-square analysis for categorical variables and 1 way analysis for continuous variables to assess for significant difference. P-value of <0.05 will be considered as statistically significant.

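### The primary outcome rule calls a fall of 3 (RPQ-3) and 10 (RPQ-13) significance with no control term or test, while the objective and the statistics section rely on a between-arm comparison

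*Protocol*

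**What the plan says.** Three places attach the word significance to an observed fall.

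- Protocol Summary, Endpoints of the study: "Significance will be observed if patients reported symptoms decrease by 3 points on the RPQ-3 and 10 on the RPQ-13".
- Section 3.5.4: "For our study significance will be observed if patients reported symptoms decreased by 3 on the RPQ-3 and 10 on the RPQ-13".
- Section 3.7.3 repeats this and then places the fall in one arm: "assigning significance if patients in the education arm have a decrease in symptom reporting on the RPQ-3 by 3 and 10 on the RPQ-13". The same sentence opens with "We will be comparing headache symptom reporting between the two groups", but the condition that follows names only the education arm.

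Two other places rely on a comparison between arms.

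- Section 3.3.2 (and the Primary Objective in the Protocol Summary) asks about the fall "in those that receive targeted headache education in comparison to those who do not". It gives no p-value.
- Section 3.7.7 states for the Rivermead, PART-O and QOLIBRI scores that "comparisons will be made between the educational arm and the current standard of care group", and takes p<0.05 as statistically significant. On method it says: "We will be using univariate Chi-square analysis for categorical variables and 1 way analysis for continuous variables to assess for significant difference".

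**The concern.** A fall of a given size in one arm is not a test of the intervention. It ignores sampling error, and it credits education with any improvement the controls also show. The objective and section 3.7.7 show that a comparison was intended, but neither puts the comparator into the rule or links 3 and 10 to the p-value. The protocol therefore states two criteria for its primary outcome and does not rank them.

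It also leaves open whether 3 and 10 apply to the arm's mean fall or are a cut-off for each patient. Section 3.7.7 provides for both categorical and continuous variables, so it does not settle this.

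At stake is the main conclusion of a randomised trial. If the threshold decides, improvement shared by both arms can make the trial positive. If controls stay unchanged, the threshold can miss a benefit that the test detects. With both criteria in the text, the choice could be made after the results are seen.

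**Working it through.** **Inputs.** From the protocol: thresholds 3 and 10; 28 evaluable patients per arm (section 3.5.6; 28/(1 − 0.20) = 35 enrolled, which reproduces); two-sided alpha 0.05. The protocol gives no SD of change, correlation between subscales or expected fall. These are assumptions: SD pairs (RPQ-3, RPQ-13) of (3, 11), (3.9, 13.1), (4.5, 15) and (6, 20); correlation r = 0, 0.5 or 0.7; normal distributions. Ranges below run over these 12 combinations.

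**Two single data sets.** Take SD 3 and 11. The standard error of a between-arm difference is SD × √(2/28): 0.802 for RPQ-3 and 2.940 for RPQ-13.

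- Education falls 3/10, controls fall 2/7: z = 1/0.802 = 1.25 (p = 0.21) and z = 3/2.940 = 1.02 (p = 0.31). The threshold is met and neither test is significant.
- Education falls 2.5/9, controls 0/0: z = 2.5/0.802 = 3.12 and z = 9/2.940 = 3.06, both p about 0.002. The threshold is missed and both tests are significant.

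**A. Arm-mean reading, no education effect.** The education-arm mean fall has standard error SD/√28. The chance that both means reach the thresholds is a bivariate normal probability.

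| True fall shared by both arms | Chance the threshold is met |
|---|---|
| 0/0 | under 0.1% |
| 1.5/5 | 0 to 4% |
| 2/7 | 0.3 to 11% |
| 3/10 | 25 to 37% |
| 4/12 | 57 to 82% |
| 4/13 | 64 to 91% |

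At 3/10 the SD drops out and the chance is 1/4 + arcsin(r)/(2π): 0.25 at r = 0, 0.333 at r = 0.5, 0.373 at r = 0.7. A two-sample t-test on change at two-sided 0.05, counted only when it favours education, is positive on either subscale in about 4 to 5% of simulated trials (at r = 0, 1 − 0.975² = 4.9%) and on both in under 1%. At a shared fall of 3/10, about 23 to 34% of trials meet the threshold with neither test significant.

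**B. Arm-mean reading, true effect 3/10, controls unchanged.** The threshold is again met in 25 to 37% of trials, because the true fall lies on it. Simulated share in which both tests are significant but the threshold is missed:

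| SD of change | Share |
|---|---|
| 3/11 | 53 to 63% |
| 3.9/13.1 | 37 to 42% |
| 4.5/15 | 26 to 27% |
| 6/20 | 8 to 10% |

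**C. Patient cut-off reading.** For one patient the standard deviation is the SD itself. With no mean change, 3 to 20% of patients in each arm meet both cut-offs. With a shared mean fall of 3/10, 25 to 37% do. A count of responders in the education arm alone therefore cannot show an education effect, and the rule names neither a comparator nor a required proportion.

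**The case against.** The strongest reply is that the objective can be read as a between-arm difference of 3 and 10. Shared improvement then cancels: even at SD 6/20 the standard errors are 1.60 and 5.35, and the chance of reaching 3 or 10 with no effect is about 3% per subscale. Section 3.7.7, the only statistics section, could supply the test, with 3 and 10 as a target size. This reading is coherent and probably close to the intent. It is not what section 3.7.3 says, however, since the condition there names only the education arm. It would still conflict with p<0.05: at SD 3 on the RPQ-3, a difference of 1.96 × 0.802 = 1.6 points is already significant. A claim without a control is not foreign to this protocol either, because the QOLIBRI objective (3.3.3.2) compares the education group with its own week-0 scores.

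The figures are also open to challenge. Scenario A is serious only if controls improve by about 3/10. Section 3.1 reports persistently high scores despite treatment, and enrolment starts at least 12 weeks after injury. On the other side, both arms receive tertiary clinic care (3.5.2.5), so shared improvement is possible. Scenario B places the true effect on the threshold, so its 25 to 37% hit rate follows by construction. Scenario C ignores the floor of the scale: entry needs an RPQ of only 3, and a patient with an RPQ-13 below 10 cannot fall by 10. These points limit the size of the problem. They do not remove the contradiction.

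Finally, whether both subscales are required, how alpha is shared and whether to adjust for baseline may belong in an SAP that is not shown. That is fair, and the finding does not rest on them.

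**Conclusion.** The concern holds and must be fixed. The protocol does not leave the primary criterion open. It states two that conflict, so an SAP that followed one would contradict the other.

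The size depends on the assumed SDs, correlations and shared falls. Used alone, the control-free threshold has a false-positive rate running from almost nil, when controls do not improve, to 25 to 37% at a shared fall of 3/10 and above that for larger falls. A between-arm test stays at about 4 to 5% throughout. When controls do not improve, the threshold can miss a true effect of 3/10 that both tests detect, in about 8 to 63% of trials. That the two criteria can give opposite verdicts on the same data depends on none of these assumptions.

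**What to change.** In the Protocol Summary (Endpoints of the study) and in sections 3.5.4 and 3.7.3:

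- State that significance is judged on the between-arm comparison, education versus standard care, of RPQ-3 and RPQ-13 at two-sided p<0.05.
- State that 3 and 10 points are the differences of interest against which the between-arm estimate and its 95% confidence interval are read.
- If a patient-level responder cut-off was meant, say so and compare the responder proportions between arms.
- Report each arm's own change descriptively only.

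Here or in the SAP, say whether both subscales must be significant (as the present wording suggests, with no split of alpha) or either suffices (with alpha shared). Adjusting for the week-0 score, which is already collected, is optional.

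The cost is wording in three places. The primary objective already states the comparison and can stand once the role of 3 and 10 is defined. Section 3.7.7 needs one line only if baseline adjustment is adopted. No new data, visits or patients are needed.

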### **3.7.4 Secondary Outcomes**

#### *Perceived Quality of Life: Quality of Life after Brain Injury scale*

The QOLIBRI (Quality of Life after Brain Injury) is a health-related quality-of-life instrument specifically developed for traumatic brain injury (TBI). The first part assesses satisfaction level with health-related quality of life (HRQOL) and is composed of 6 overall items and 29 items assigned to 4 subscales: thinking, feelings and emotion, autonomy in daily life and social aspects. The second part is devoted to "bothered" questions and composed of 12 items in 2 subscales: negative feelings and restrictions. Responses to the 'satisfaction' items (i.e. items on the Cognition, Self, Daily Life & Autonomy, and Social Relationships scales) are coded on a 1 to 5 scale, where 1= "not at all satisfied" and 5="very satisfied". Responses to the 'bothered' items (i.e. items on the Emotions and Physical Problems scales) are reverse scored to correspond with the satisfaction items, where 1="very bothered" and 5="not at all bothered".

Using this scale, we hope to capture whether or not patients believe they play an active role in their health and whether or not they feel empowered to alter their health status. It will hopefully also allow us to capture what barriers there are to a patient's recovery in regards to what negative feelings and limits they perceive; preventing them from making a meaningful recovery.

#### *Perceived Function in Society: Participation Assessment with Recombined Tools-Objective*

The Participation Assessment with Recombined Tools-Objective (PART-O) is an outcome scale measuring participation in the community. The PART-O consolidates questions from 3 commonly used instruments, and measures 3 domains of community participation post rehabilitation: Productivity, Out and About, and Social Relations; it is an objective measure of participation, representing functioning at the societal level. It asks questions like, *in a typical week, how many hours do you spend working for money, whether in a job or self-employed?* The PART-O was developed to examine long-term outcomes and can also be used to evaluate the effectiveness of interventions to improve social/societal functioning. The z-scores can be used to provide the basis for an assessment of progress in post-acute rehabilitation, allowing for an assessment of intra-individual differences in change across domains as well as inter-individual comparisons with the normative groups. When patients are using this tool, we will use this opportunity to ask about current employment status. We will use this tool in our study to assess to what degree do patients feel that they are able

to perform their activities of daily living. Along with how close do they believe they are to returning to premorbid level of functioning versus adjusting to their new health status.

#### *Access to Medical Services*

Tracking patient's utilization of health care services during the time of the study is an important outcome that this study hopes to measure. The aim is to see if education can ultimately reduce unnecessary access to medical care. As stated previously we hope to accomplish this by providing information to patients on red flags and when to seek medical advice. Patients will be asked to recall the number of times they have sought out medical attention since they were last seen in the subspecialty clinic. This includes walk-in clinics, hospitals, their family MD, telehealth and ER visits. Future goals after this study has been completed would be to use the ICES database to quantify the utilization of health care services in this subset patient population.

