#### **3.3.3 Secondary Objectives**

##### **3.3.3.1 Key Secondary Objectives**

When and what type of health care services do participants in this study access, how frequently and is there a difference and between the two groups.

[figure not shown]

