#### **3.5.5 Secondary Outcome Measures**

For the secondary endpoints, we will analyze the frequency and type of health care patients accessed outside of their current standard of care during the 12-week study period. This will be compared to our controls and will include emergency room, family physician visits, hospital admissions and telehealth that are related to post traumatic headache symptoms.

Another end point we are interested in exploring is whether patients that are provided targeted headache education along with tertiary care has an increased frequency of social interactions in comparison to patients receiving the current standard of care. We are very interested in the hours that each patient devotes to their previous work or hobbies and we will be comparing this once again to patients in the clinic who are receiving the standard of care. This outcome will be measured using the PART-0 tool which asks questions about the type and frequency of social engagements that patients may encounter each week along with the hours that patients devote to returning back to work, school or homemaking.

Lastly, we are interested in whether or not education and reassurance alter a patient's perceived quality of life after a mild-traumatic brain injury. This will be analyzed by using the QOLIBRI (Quality of Life after Brain Injury). Using this scale we hope to capture whether or not patients believe they play an active role in their health and whether or not they feel empowered to alter their health status. It will hopefully also allow us to capture what

barriers there are to a patient's recovery in regard to what negative feelings and limits they perceive; preventing them from making a meaningful recovery.

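### The key secondary outcome is headache-related health-care use, but the only stated collection rule is a recalled count with no reason or date for each contact

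*Protocol*

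**What the plan says.** Four places in the Protocol describe this outcome.

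- **Objective (3.3.3.1, repeated in the Protocol Summary).** The only key secondary objective asks "When and what type of health care services do participants in this study access, how frequently", compared between the groups.
- **Endpoint (3.5.5).** Here "we will analyze the frequency and type of health care patients accessed outside of their current standard of care during the 12-week study period". The comparison with controls is to include "emergency room, family physician visits, hospital admissions and telehealth that are related to post traumatic headache symptoms".
- **Collection (3.7.4, Access to Medical Services).** "Patients will be asked to recall the number of times they have sought out medical attention", counted from the last visit to the subspecialty clinic. The settings follow: "This includes walk-in clinics, hospitals, their family MD, telehealth and ER visits". Administrative data are left for later: "Future goals after this study has been completed would be to use the ICES database to quantify the utilization of health care services".
- **Analysis (3.7.7).** Frequency and type of care are to be analysed. Neither timing nor relation to headache is mentioned.

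**The concern.** The objective, the endpoint and the collection rule describe three different quantities. The endpoint needs the reason for each contact, the objective also needs its date, and the collection rule asks for neither. If the forms follow 3.7.4 as written, a family-doctor visit for an unrelated matter counts the same as a headache visit.

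A statistical analysis plan cannot repair this. It can choose a model, but it cannot recover a reason or a date that was never asked for. At stake are the interpretability of the one outcome designated key among the secondary objectives, and the sensitivity of its group comparison.

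**Working it through.** No stated figure is at issue, so the check sets the texts side by side.

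| Element | Objective (3.3.3.1) | Endpoint (3.5.5) | Collection (3.7.4) | Analysis (3.7.7) |
|---|---|---|---|---|
| Number of contacts | yes | yes | yes | yes |
| Type of service | yes | yes | settings listed; recoverable if counted per setting | yes |
| Timing | yes | no | no date asked | no |
| Related to headache | not stated | yes | no reason asked | no |
| Period | not stated | 12-week study period | since last subspecialty clinic visit | not stated |
| Walk-in clinics | not stated | not named | named | not stated |

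**Could another stated source fill the gaps?**

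- Sections 3.5.2.2 and 3.8.1 name the RPQ, PART-O and QOLIBRI, with demographics and history at baseline. They name no item on health-care use.
- The list in 3.9 describes the baseline and follow-up questionnaires by the same three instruments. It also lists a Post Concussion Headache Assessment, whose content is not shown.
- The exit interview in 3.5.2.1 has no stated content and is described under the educational intervention.
- Controls are surveyed only at weeks 0 and 12 (3.5.2.2 and 3.7.1), so timing cannot be read from repeated surveys.
- The ICES database is reserved for work after the trial.

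No stated source supplies a reason or a date.

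**What unrelated contacts would do.** The protocol gives no contact rates, so the rates here are assumptions that show the mechanism only. Take 2 headache-related contacts per control patient and 1 per educated patient over 12 weeks, plus *u* unrelated contacts per patient in both arms. Counts are taken as Poisson, with 28 patients per arm (the number before the attrition allowance in 3.5.6).

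- Ratio of means = (1 + u)/(2 + u).
- Difference in means = (2 + u) − (1 + u) = 1 for every u.
- Standard error of the difference = √[((2 + u) + (1 + u))/28] = √[(3 + 2u)/28].
- Power for the log ratio = Φ(|ln ratio|/SE − 1.96), with SE = √[1/(28(2 + u)) + 1/(28(1 + u))].

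| u | Ratio | Difference | SE of difference | Power (log ratio) |
|---|---|---|---|---|
| 0 | 0.50 | 1 | √(3/28) = 0.33 | 85% |
| 1 | 0.67 | 1 | √(5/28) = 0.42 | 65% |
| 2 | 0.75 | 1 | √(7/28) = 0.50 | 51% |
| 4 | 0.83 | 1 | √(11/28) = 0.63 | 36% |

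On a ratio scale the effect shrinks toward 1. On a difference scale it stays the same and only precision falls. Section 3.7.7 names a one-way analysis for continuous variables, which compares means, so loss of precision is the consequence closer to the stated analysis.

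**The case against.** The strongest reply is that the forms are not shown. Section 3.7.1 points to the appendices for the full surveys, and the contents listed in 3.9 omit any health-care item although 3.7.4 says patients will be asked. Either that list is incomplete or the question sits on another form, which might hold reason and date. This stands as a limit: what cannot be derived is what the stated rule leaves out. If the fields exist, 3.7.4 misdescribes the collection and still needs correcting.

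Four stronger readings are tempting, and the document does not support them.

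- *The trial will knowingly compare all-cause contacts and call them headache-related.* Section 3.5.5 carries the headache restriction, and no text orders unrelated visits to be counted. Section 3.7.4 is silent on the reason.
- *A defined timing endpoint is lost.* Timing appears only in the objective; the endpoint and analysis text speak of frequency and type. It is an element of the objective that was never carried forward.
- *Walk-in visits are collected but excluded from the endpoint.* The list in 3.5.5 is introduced by wording that need not be exhaustive, and 3.1 names walk-in clinics among the visits to be reduced. The lists differ and should match, but no exclusion is stated.
- *A third to two thirds of the effect is lost.* The ratios 0.67, 0.75 and 0.83 against 0.50 do give 1 − (1 − ratio)/0.5 = 33%, 50% and 67%. That rests on assumed rates and on a rate ratio the protocol never names. It also assumes that education leaves unrelated contacts unchanged, although the sessions cover when to seek care.

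One further objection stands and shapes the fix. Headache education may change how patients label a visit, so an attributed count can differ between arms for reasons other than use. An all-cause count avoids this.

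**Conclusion.** The point holds as a mismatch within the current text. Under the collection rule in 3.7.4, contacts related to post-traumatic headache cannot be separated from others, and the timing asked for in 3.3.3.1 has no data and no place in 3.5.5 or 3.7.7. Type of service is recoverable if the count is taken per setting.

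The size of the effect on the comparison is unknown. Its direction is more noise and, on a ratio scale, a pull toward no difference, provided that education does not change unrelated contacts. The conclusion rests on the protocol's wording, with the forms unseen. The outcome is secondary but designated key, and the gap is cheap to close only while data can still be collected, so the change should be made.

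**What to change.** In the week-12 survey, identically in both arms, record for each contact since week 0:

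1. the type of service;
2. the approximate study week;
3. whether it was for post-traumatic headache (yes/no).

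Report headache-related contacts as the endpoint defined in 3.5.5, with all-cause contacts alongside because attribution may differ between arms. Starting at week 0 also aligns the recall period with the 12-week endpoint. Use one list of services in 3.5.5 and 3.7.4 that names walk-in clinics, and state in 3.5.5 and 3.7.7 how timing will be used.

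If reason and date will not be collected, restate the objective and endpoint as an all-cause count by setting and remove timing from the objective. If the existing forms already hold these fields, correct 3.7.4 to say so.

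The cost is three REDCap fields per reported contact and a wording amendment. The survey becomes slightly longer, and attribution rests on the patient's report.
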